5. STUDY POPULATION

1212 subjects will be randomized in the study.

Patients are eligible for enrollment into the study if they meet all of the inclusion criteria and do not meet any of the exclusion criteria.

5.1. Inclusion Criteria

1. Healthy male or non-pregnant female aged ≥ 35 years with a clinical diagnosis of OA of the knee according to the American College of Rheumatology (ACR) criteria² i.e. Knee pain along with at least 3 of the following 6 criteria
 - a. Age > 50 years
 - b. Stiffness < 30 minutes
 - c. Presence of crepitus
 - d. Bony tenderness
 - e. Bony enlargement
 - f. No palpable warmth
2. Symptoms in target knee for at least 6 months prior to screening
3. Knee (not referred) pain in target knee for 15 days of the preceding month (periarticular knee pain due to OA and not due to other conditions such as bursitis, tendonitis, etc.)
4. Pain in the target knee requiring the use of NSAIDs or acetaminophen/paracetamol (topical or oral treatments).

5. Subject having an X-ray of the target knee, taken no more than 1 year before baseline, showing evidence of OA with Kellgren-Lawrence grade 1-3 disease.
6. After discontinuing all pain medications (placebo run – in period) for at least 7 days, had at least moderate pain on movement (POM) for target knee, defined as a baseline score of ≥ 50 mm on a 0-100 mm Visual Analog Scale (VAS) immediately prior to randomization
7. After discontinuing all pain medications (placebo run – in period) for at least 7 days has a baseline Western Ontario and McMaster Universities Osteoarthritis Index (WOMAC Likert (version 3.1)) pain subscale of ≥ 9 immediately prior to randomization.
8. Able to tolerate rescue medication with acetaminophen (paracetamol) taken as 1-2 tablets up to a maximum 2 gm per day for the duration of the study.
9. Subjects who can read and understand WOMAC pain sub scale.
10. If female, patient must be either postmenopausal for at least one year prior to randomization, surgically sterile (bilateral tubal ligation, bilateral oophorectomy or hysterectomy), or practicing the following methods of birth control:
 - a) Oral Contraceptives or Intrauterine Device in place for at least 3 months prior to the start of the study and remaining in place during the study period, or
 - b) Double Barrier methods containing or used in conjunction with a spermicidal agent, or
 - c) Contraceptive Patches/ Implants, or
 - d) Abstinence: Subjects who will be practicing abstinence will agree to have a documented second acceptable method of birth control if the subject become sexually active during the course of her study participation.

5.2. Exclusion Criteria

1. Pregnant or lactating or planning to become pregnant during the study period.
2. X-ray showing evidence of OA with Kellgren-Lawrence grade 4 disease.
3. History of OA pain in the contralateral knee requiring medication (OTC or prescription) within 1 year prior to screening.
4. After discontinuing all pain medications (placebo run-in period) for at least 7 days, had a baseline score of ≥ 20 mm on a 0-100 mm Visual Analog Scale (VAS) for the contralateral knee immediately prior to randomization.
5. History of OA of either Hip or Hands
6. History of secondary OA (e.g. congenital, traumatic, gouty arthritis), rheumatoid arthritis.
7. History of chronic inflammatory disease (e.g., colitis) or fibromyalgia.
8. History of Drugs or Alcohol abuse within the previous year.
9. Symptomatic peripheral vascular disease of the study leg (prior or current).
10. Any musculoskeletal condition that would impede measurement of efficacy at the target knee.
11. History of regular headaches or backache which warrants often use of acetaminophen (paracetamol) within the previous year.

12. Concomitant skin disease at the application site which may affect study drug application or tolerability evaluation.
13. History of active asthma within the previous year that may require periodic treatment with systemic steroids during the study period (note: inhaled steroids for this condition are allowed).
14. History of aspirin sensitive asthma.
15. History of uncontrolled hypertension (blood pressure more than 150/100 mm of Hg) in spite of treatment within the previous year.
16. History of myocardial infarction, thrombotic events, stroke, congestive heart failure, impaired renal function (Serum creatinine $> 1.5 \times$ ULN) or liver disease within the previous year.
17. History of coronary artery bypass graft within 6 months of screening.
18. History of gastrointestinal bleeding or peptic ulcer disease in last one year.
19. Known allergy to aspirin, nonsteroidal anti-inflammatory drugs (NSAID) or acetaminophen (paracetamol).
20. Elevated transaminases (≥ 3 times ULN) and Hemoglobin < 9.0 g/dL at screening.
21. Viscosupplementation in any joint including the target knee within 6 months prior to screening
22. Receiving physical therapy (at an outpatient/clinic setting) for the lower extremities or having received physical therapy for the lower extremities within 1 month before screening.
23. Use of anticoagulants, ACE-inhibitors, cyclosporine, diuretics, lithium, or methotrexate prior to 30 days of screening.
24. Concomitant use of intra articular corticosteroids, systemic corticosteroids, topical corticosteroids, or immunosuppressive drugs or their use prior to 30 days of screening.
25. Concomitant acetylsalicylic acid therapy other than a stable low dose used for cardiac prophylaxis (maximum 162 mg daily)³ taken for at least 3 months prior to enrollment and maintained throughout the duration of the study.
26. History of major surgery or previous damage to the study knee at any time, or minor knee surgery (e.g. any surgery other than major surgery including, but not limited to, cartilage repair, collateral ligament repair, or arthroscopic debridement) to the study knee within 1 year prior to screening.
27. Known history of positive HIV, HCV, or HBsAg.
28. Tense effusion requiring aspiration.
29. Subjects who have been treated with an investigational drug or investigational device within a period of 30 days prior to enrollment.
30. Any other acute or chronic illness that could compromise the integrity of study data or place the subject at risk by participating in the study.

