2.5. Contraindications

- Known hypersensitivity (e.g., anaphylactic reactions and serious skin reactions) to diclofenac or any components of the drug product¹¹
- History of asthma, urticaria, or other allergic-type reactions after taking aspirin or other NSAIDs. Severe, sometimes fatal, anaphylactic reactions to NSAIDs have been reported in such patients¹¹
- In the setting of coronary artery bypass graft (CABG) surgery¹¹

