7.2 Investigational Product Labeling, Packaging & Formulation

Study drugs will be packaged and labeled based on the randomization schedule generated prior to the start of the study. The investigator will be overall responsible for ensuring that IPs are stored in a safe, limited access location, as per the condition noted in the label. Each site will receive the pre-labeled study drugs for the run-in period and treatment period.

Labelling text will be compliant with local regulatory requirements. The label should include but not be limited to: Sponsor name/address, Dosage, route of administration, name/strength, batch number/code, study reference or protocol number, kit's number, directions for use, statement 'for clinical trial use only', storage conditions, expiry/use by date.

At the start of placebo run-in period and at baseline visit, each subject will receive the study drugs and at the baseline visit, subjects will receive the rescue medications.

Formulation Details

Test Formulation	Active ingredient: Diclofenac sodium Inactive ingredients: [REDACTED] [REDACTED] [REDACTED] [REDACTED]
Reference Formulation	Active ingredient: Diclofenac sodium Inactive ingredients: Carbomer homopolymer Type C, cocoyl caprylocaprate, isopropyl alcohol, mineral oil, polyoxyl 20 cetostearyl ether, propylene glycol, purified water, and strong ammonia solution
Placebo Formulation	It will contain all the excipients (inactive ingredients) present in the test formulation.

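### Section 2.5 of the protocol lists hypersensitivity to any component of the gel as a contraindication, but no entry criterion names allergy to a gel component

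*Protocol*

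**What the plan says.** Protocol section 2.5 (Contraindications) opens its list with "Known hypersensitivity (e.g., anaphylactic reactions and serious skin reactions) to diclofenac or any components of the drug product". The list is referenced to the prescribing information of the Reference gel.

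Exclusion 19 in protocol section 5.2, repeated in the same words in the synopsis, reads "Known allergy to aspirin, nonsteroidal anti-inflammatory drugs (NSAID) or acetaminophen (paracetamol").

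Protocol section 5 makes entry depend on the numbered criteria: "Patients are eligible for enrollment into the study if they meet all of the inclusion criteria and do not meet any of the exclusion criteria".

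On what the gels contain, protocol section 7.2 names the Reference excipients, among them "isopropyl alcohol, mineral oil, polyoxyl 20 cetostearyl ether, propylene glycol". Of the placebo gel it says: "It will contain all the excipients (inactive ingredients) present in the test formulation". The Test list itself is blacked out.

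**The concern.** The entry criteria appear to have been built in part from the contraindications, and one part was not carried across. Allergy to the rescue tablet is screened for, but allergy to the constituents of the gel under study is not. If that is an oversight, a site applying the criteria exactly as written could enrol a person to whom the protocol's own contraindication applies. That person would apply gel four times daily for at least 7 days of run-in and then for 4 weeks of treatment. Protocol section 2.8 names application site reactions, including dermatitis, as the most common adverse reactions, and application site reaction is one of the two safety endpoints in protocol section 12.4 and SAP section 4. At stake are the protection of a few subjects and consistency between sites in handling a recorded excipient allergy.

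**Working it through.** The point is a comparison of texts, and no arithmetic is involved. The steps are to trace each element of section 2.5 into the criteria, look for any other criterion that could catch the case, and follow a hypothetical subject through the visits.

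**Tracing section 2.5 into section 5.2**
- Hypersensitivity to diclofenac: covered by exclusion 19, because diclofenac is an NSAID.
- Asthma, urticaria or other allergic-type reaction after aspirin or another NSAID: covered by exclusion 19 and by exclusion 14, "History of aspirin sensitive asthma".
- Coronary artery bypass graft setting: addressed by exclusion 17.
- Hypersensitivity to any other component of the product: no counterpart.

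Acetaminophen allergy, which comes from the rescue-medication warnings in section 2.9, is also carried into exclusion 19. The component clause is thus the only element left without a counterpart, and no reason is given.

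**Looking for another criterion**
- All 10 inclusion and 30 exclusion criteria were read in the synopsis and in sections 5.1 and 5.2. None names allergy to the gel or to an excipient.
- Exclusion 12 is the nearest on skin: "Concomitant skin disease at the application site which may affect study drug application or tolerability evaluation". It needs skin disease present at the site, so a known contact allergy with clear skin does not meet it.
- Exclusion 30 is the general clause on other acute or chronic illness that could compromise the data or place the subject at risk. It names neither allergy nor excipients, so it applies only if an investigator chooses to regard a known sensitivity as such an illness.
- The withdrawal criteria in section 7.7 operate after a reaction has occurred.
- The SAP adds no eligibility criterion. Its mITT and PP populations (SAP sections 6.5 and 6.6) refer back to the same criteria.

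**Following a subject**
Take someone with a known allergy to propylene glycol, a listed Reference excipient, and healthy skin at screening, who otherwise qualifies.
1. At Visit 1 the medical history may record the allergy, but no numbered criterion tells the site to act on it.
2. At Visit 2 the subject starts placebo gel, which carries the Test excipients. The first application is supervised.
3. At Visit 3 eligibility is reviewed again, against the same criteria, and the application site is assessed.
4. From Day 1 the subject applies randomised gel at home.

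Read strictly, the section 5 rule makes this subject eligible at each review.

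**The case against.** Section 2.5 is background. It sits in the introduction and restates Reference labelling, so this is a mismatch between background and operative text and not a conflict between two trial rules. That stands, and it sets the tone of the fix. It does not remove the gap, since the protocol presents the contraindication for a product that it then administers.

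Exclusion 30 could reasonably be used by a careful investigator, and there are other safeguards: the screening history, the supervised first run-in application, the repeated eligibility reviews and the option to stop for an adverse event. These limit harm, but they depend on judgement or act after exposure. The diary instructions in Appendix I and the consent form are not in the text available for this review, so it cannot be said that subjects are never asked about ingredient allergy.

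Three stronger readings are tempting, and the documents support none of them.
- A reader might infer that the tolerability comparison is tilted, on the argument that the run-in exposes subjects to Test excipients, so reactors to Reference-only excipients first react after randomisation and in one arm. This requires excipients found only in the Reference, which the blacked-out Test list does not let anyone confirm. No rule removes run-in reactors, and withdrawal for an adverse event is discretionary. SAP section 7.12.1.1 only summarises application site reactions, with no test between arms.
- A reader might attach a count. An assumed rate of 0.5% to 2% gives 0.005 × 1212 ≈ 6 to 0.02 × 1212 ≈ 24 subjects, or about 2 to 8 per arm. No such rate is in the documents, and the calculation ignores exclusion 30, the screening history and attrition in the run-in.
- A reader might infer damage to the primary analysis. Nothing in the documents shows an effect on the equivalence or superiority tests.

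**Conclusion.** The gap is real and minor. The criteria as written allow enrolment and dosing of a subject with a known allergy to a gel excipient, although section 2.5 lists that as a contraindication. The conclusion rests on reading the numbered criteria as the operative test of eligibility, as section 5 states, and on not stretching exclusion 30 to cover a sensitivity that is not currently causing disease. It does not depend on what the Test gel contains. The number of subjects affected is unknown. The case for change rests on subject protection and uniform site practice; an imbalance in local tolerability remains a conditional possibility only.

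**What to change.** Reconcile exclusion 19, in section 5.2 and in the synopsis, with section 2.5, so that the entry criteria reflect the contraindication that the protocol states for the gels it administers. Because section 2.5 speaks of a single drug product and cites Reference labelling, the reconciled text should make clear which gels' components are meant. Sites then need to know those components at screening, in a form that preserves the blind and any confidentiality of the Test formulation.

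The cost is one clause and one screening question. No new procedure is needed, the sample size and the SAP analyses are unchanged, and very few subjects should be lost.

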6. RANDOMIZATION AND BLINDING PROCEDURES

6.1. Randomization Procedure

A computerized randomization will be generated by an independent third party (not involved in the packaging and labelling of the study medication).

Subjects will be randomly assigned in 1:1:1 ratio in three groups. Treatment allocation can be either Mylan's Diclofenac Sodium Topical Gel 1%, Voltaren® Gel 1% (Reference Listed Drug), or Placebo. A balanced randomization schedule will be generated using SAS® software (Version: 9.1 or higher; SAS Institute Inc., USA). The randomization code will be held by an independent third party throughout the conduct of the study in order to minimize bias.

A sealed copy of the randomization code for each kit provided under separate cover inside the block will be retained at investigational site. It should be available to FDA investigators at the time of site inspection to allow for verification of the treatment identity of each subject.

6.2. Blinding Procedure

Placebo run-in period will be single blinded in which subjects will not be aware of the treatment given.

Treatment period will be double blinded in which all the investigators, subjects, site staff, CRO team, study monitors, laboratory personnel and/or other designated individuals will be blinded to the medication codes. The formulation of test, reference and placebo investigational products would be identical in appearance to make any difference in treatment less obvious to the subjects and to maintain adequate blinding of evaluators.

Unblinding will be performed by a designated person in case of SAE or other significant events (Refer [section 11.2.5.3](#)). The event of unblinding shall be documented in the source notes.

Mylan Product Safety and Risk Management (PSRM) can unblind the treatment assignment for any subject with a SAE which qualifies for the unblinding based on country specific regulatory requirements.

The event of unblinding shall be documented in the source notes. Reasons for treatment unblinding must be clearly explained and justified in the eCRF. The date on which the code was broken together with the identity of the person responsible must also be documented.

If a subject's treatment assignment is unblinded for any reason then the subject should be withdrawn from the study.

7. STUDY TREATMENT, DESCRIPTION AND ALLOCATION

7.1 Investigational Medicinal Products and Non - Investigational Medicinal Products (IMP and NIMP)

Investigational Medicinal Products (IMP)

The study medication supplied by the sponsor will consist of:

Treatment Arms	Intervention
Test product:	Diclofenac Sodium Gel, 1% manufactured by Mylan Inc.
Reference product:	Voltaren® Gel (Diclofenac Sodium Topical Gel) 1% manufactured by Novartis Pharma Produktions GmbH, marketed by: Endo Pharmaceuticals Inc., Malvern, PA 19355
Placebo formulation:	Placebo gel [REDACTED].

Identical dosing cards will be provided along with the investigational medicinal products.

Non-Investigational Medicinal Products (NIMP)

Acetaminophen (paracetamol) tablets will be given to all the subjects baseline for use as a rescue medication or for the treatment of aches and pains unrelated to knee pain such as headache during treatment period.

7.2 Investigational Product Labeling, Packaging & Formulation

Study drugs will be packaged and labeled based on the randomization schedule generated prior to the start of the study. The investigator will be overall responsible for ensuring that IPs are stored in a safe, limited access location, as per the condition noted in the label. Each site will receive the pre-labeled study drugs for the run-in period and treatment period.

Labelling text will be compliant with local regulatory requirements. The label should include but not be limited to: Sponsor name/address, Dosage, route of administration, name/strength, batch number/code, study reference or protocol number, kit's number, directions for use, statement 'for clinical trial use only', storage conditions, expiry/use by date.

At the start of placebo run-in period and at baseline visit, each subject will receive the study drugs and at the baseline visit, subjects will receive the rescue medications.

Formulation Details

Test Formulation	Active ingredient: Diclofenac sodium Inactive ingredients: [REDACTED] [REDACTED] [REDACTED] [REDACTED]
Reference Formulation	Active ingredient: Diclofenac sodium Inactive ingredients: Carbomer homopolymer Type C, cocoyl caprylocaprate, isopropyl alcohol, mineral oil, polyoxyl 20 cetostearyl ether, propylene glycol, purified water, and strong ammonia solution
Placebo Formulation	It will contain all the excipients (inactive ingredients) present in the test formulation.

7.3 Storage Conditions

Study medication should be stored, prior to dispensing, at controlled temperature 20°C to 25°C (68°F to 77°F) in a locked, limited access area at the study center. Do not freeze the product. Dosing card should be stored along with study medication. After dispensing, the subject will be instructed to store the medication at 20°C to 25°C (68°F to 77°F) [USP Controlled Room Temperature]. Used/unused medications except the retention samples, will be handled as per instructed by the sponsor.

7.4 Investigational Product Handling and Management

The medication will be supplied in tubes as a kit. The tubes will be packed and labeled according to the randomization scheme generated prior to the start of the study. The containers/kit should not be opened by the subject at the study center.

Details of the IP handling will be described in 'IP Handling Work Instruction'.

7.5 IP Retention Requirements

The sponsor will supply sufficient quantities of the study formulation for the following: 1) completion of the study and 2) retention, as per applicable regulations. All drug supplies provided for this study will be stored in a secure area with restricted access, under storage conditions described in the reference drug package labeling.

Details of the IP retention will be described in 'Investigational Product Retention Plan'.

Records will be made of receipt and dispensing of study drugs supplied. It is the responsibility of the Sponsor to ensure that all drug supplies provided for the study are manufactured under current Good Manufacturing Practices (cGMP) and are suitable for human use.

Upon completion or termination of the study, a sample of all study supplies will be retained for a period of at least 5 years following the date on which the study is approved by USFDA or, if the study is not approved, at least 5 years following the date of completion of the study in which the investigational products were used. Retention samples should be randomly selected from the drug supplies received prior to dispensing to subjects. Retention samples should not be returned to the sponsor or CRO at any time.

7.6 Study Medication Administration

At the start of the placebo run-in period, placebo gel will be dispensed and during the treatment period, Mylan's Diclofenac Sodium Topical Gel 1%, Voltaren® Gel 1% (Reference Listed Drug), and Placebo gel will be dispensed to the qualified subjects for the application of gel to the target knee. Target knee means the knee, which is more painful, will be identified during the screening visit. First administration of the study drug at the start of placebo run-in period will be supervised at the study center, with subsequent applications self-administered on an outpatient basis.

Subject diary will be given at the start of the placebo run-in period and treatment period to the subjects containing instructions related to the proper administration method (see [Appendix I](#)).

Method of application during run-in period and treatment period:

Study participants will have to apply 4 gm of study medication to the affected area of target knee 4 times daily. The proper amount of gel will be measured using the dosing card. The gel will be applied within the rectangular area of the dosing card up to 4 gm line. [REDACTED]

[REDACTED]

[REDACTED].

[REDACTED]

[REDACTED]

[REDACTED]

[REDACTED]

[REDACTED]

[REDACTED]

Rescue Medication Administration:

Subjects will be allowed acetaminophen (paracetamol) tablet as rescue medication on an as-needed basis (up to 2 gm/ day) during the treatment period, except for the at least 3 days prior to each clinic visit.

